11.4.1 Datasets to be analysed, analysis populations

All analyses will be done on the intention-to-treat principle set whereby all randomized patients will be analyzed in the allocated group. This means regardless of any protocol violations such as participants in the control group purchasing an ENDS on their own or early treatment discontinuations in the intervention group.

11.4.2 Primary Analysis

To answer the primary research question, we will compare the rates of quitting among smokers randomized to ENDS vs. those receiving usual care, on an intention-to-treat basis. Continuous smoking cessation from target quit date will be the main outcome, confirmed by biomarkers of exposure (anabasine). We will calculate quit rates, relative risks (RR), and absolute risks for ENDS +SOC (intervention group) compared to SOC alone (control group). We will further compare groups using multivariate regression models adjusting for appropriate co-variates. Participants who stopped smoking, and who are continuous ENDS users, will be considered quitters.

11.4.3 Secondary Analyses

We will repeat the calculations described in 11.4.2 for the secondary smoking cessation outcomes. To test the effect of ENDS on reducing the number of cigarettes smoked per day, we will define a binary predictor of >50% smoking reduction from baseline to follow-up smoking and repeat the analyses for the main outcome of quitting. We will also use joint multivariate random-effects (JMRE) models allowing to model CPD and smoking cessation. In addition, we will use mixed linear effect model to analyze the change in CPD modelled as a continuous outcomes over time.

We will present modified per-protocol sensitivity analyses, in particular for participants in the control group who might have started using ENDS in the first six months.

For the measures of changes in measures of urinary biomarkers, exhaled breath measures, CVRFs and respiratory symptoms and pulmonary function from baseline to the 6-months visit, we will first compare the changes in these measures between the intervention and control group using two-sample t-tests or Wilcoxon rank-sum test, whenever appropriate. We will then fit univariate and multivariate mixed linear effect models. We will use multivariate linear and multinomial logistic regression models to compare groups according to their exposure to tobacco smoking and ENDS.

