For measures of carcinogenicity, such as measures of incomplete combustion agents (VOCs and PAH: 1-OHP, 1- and 2-NAPH in urine)^{29,30} and exposure to TNSAs (NNK and NNN in urine),¹⁸ and measures of oxidative stress in urine (8-OHdG and 8-isoprostane),^{41, 91, 164} and MN in buccal epithelium, we will compare groups that stopped smoking with or without ENDS in intention to treat analyses (Ai+Ci vs. Ac+Cc; 112 vs. 70) and in per protocol analyses (Ai+Ac vs. Ci+Cc; 65 vs. 117). Based on previous cross sectional studies contrasting past smokers to smokers,^{52, 164, 165} we estimate a 48% power to detect significant differences between quitters and continuing smokers for 8-OHdG and 100% for 8-isoprostane between baseline and follow-up, at alpha 0.05 and an assumed correlation between baseline and follow-up of 0.7 (Table 11.2-2). We will perform 3 determinations of buccal MN on 2000 cells for each participant. Based on published results,^{99, 100, 166-168} we expect a baseline frequency among non-smokers of 0.74 MNs per thousand cells and a between-subject GSD of 1.3. We will have 80% power to detect a significant difference between smokers and non-smokers for a frequency ratio (FR) of 1.5.

For the 6-months changes in cardiovascular risk factors, we do not have direct data from RCT of ENDS use. Using data from previous RCT on nicotine replacement therapy, we expect a mean increase in HDL-cholesterol of 0.107 mmol/l (95% confidence interval 0.057 to 0.158 mmol/l) among quitters,⁵⁴ an increase in systolic blood pressure of 1.65 mm Hg and in diastolic blood pressure of 0.90 mm Hg after 6 months in quitters.^{55, 56} Considering data from the CoLaus study, a study on cardiovascular risk factors in a random sample of the Lausanne population, we expect to only have a 10 to 40% chance to detect a difference between ENDS users and continuing smokers.¹⁶⁹ We expect to be able to have 100% power to detect changes in respiratory symptoms.^{8, 170}

We do not expect to have adequate power to detect changes in incidence of cancer. However, we will apply strict open access rules and post the data on rigorous and systematic assessment of self-reported cancer in an online repository to enable the international community to pool results with other datasets and answer more definite answers on these important outcomes

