Table 11.2-2: Power calculation and sample size required to detect statistically significant differences between past- and current smokers for secondary outcome measures

Measure	Matrix	Non smoker	Past smoker	Current smoker	Reference	Power * N **	
		Mean (SD)	Mean (SD)	Mean (SD)			
Inhaled compounds							
1-OHP	Urine [µg/g creat]	0.08 (0.11)	0.11 (0.11)	0.2 (0.25)	Bartolomé et al. 2015 ¹⁷¹	98%	37
	Urine [µg/g creat]		0.04 (0.002)	0.12 (0.005)	Naufal et al. 2011 ¹⁷²	100%	2
1-naphtol	Urine [ng/g creat]		1.6 (0.1)	7.2 (0.4)	Naufal et al. 2011 ¹⁷²	100%	2
2-naphtol	Urine [ng/g creat]		1.8 (0.05)	8.9 (0.5)	Naufal et al. 2011 ¹⁷²	100%	2
Oxydative stress							
8OHdG	Urine [ng/mg creat]	2.75 (1.6)	3.62 (2.41)	4.24 (3.3)	Sauvain et al., 2011 ¹⁶⁴	48%	174
	EBC [ng/ml]	0.36 (0.09)	0.31 (0.10)	0.52 (0.15)	Doruk et al., 2011 ⁹¹	100%	3
8-isoprostane F2a	Urine [µg/g creat]	0.51 (0.04)	0.74 (0.07)	1.1 (0.1)	Harman et al., 2003 ⁵²	100%	2
	Urine [µg/g creat]	0.7 (2.7)		4.48 (2.7)	Seet et al., 2011 ⁴³	100% [†]	5
	EBC [pg/ml]	10.8 (0.8)		24.3 (2.6)	Montuschi et al., 2000 ⁸⁹	100% [†]	2

*Power to detect statistically significant difference between quitters (past smokers) and continuing smokers (current smokers) between baseline and follow-up at alpha 0.05, an assumed correlation between baseline and follow-up of 0.7 and 182 participants (112 vs. 70) for urine analyses.

† Calculations above in * based on data from never smokers compared to current smokers.

** Number of participants per group needed to detect statistically significant differences at alpha of 0.05 and beta (power) of 0.80.

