11.4 Planned Analyses

The statistical analysis of the main results of the trial will be done at CTU Bern by a statistician blinded to the allocation. After the start of the trial but before recruitment ends, a statistical analysis plan will be written. The plan will determine all necessary data preparation steps (e.g. additional validations, generation of new variables), definitions (e.g. analysis sets), and statistical analyses (e.g. models, outputs such as tables and graphs).

All statistical analyses will be presented as effect measure plus 95% confidence interval. A significance level of 5% will be used.

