4.1 Confidence intervals and *P* values

All applicable statistical tests will be 2-sided and will be performed using a 5% significance level. Estimates and effect measures will be presented with a two-sided 95% confidence interval.

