6.3 Analysis methods

6.3.1 Primary analysis

The primary analysis is based on the treatment policy estimand, using the full analysis set according to the intention to treat principle.

The primary outcome will be presented as proportion with 95% Wilson confidence interval in each intervention group and compared between groups using the chi-square test. The effect size will be presented as relative risk with 95% Koopman confidence interval, as well as risk difference with 95% Newcombe-hybrid-score confidence interval.

Secondary smoking outcomes will be analysed as the primary outcome.

Continuous secondary outcomes will be analysed using linear models, adjusted for the outcome measure at baseline, if it is available. Missing values in continuous outcomes will be imputed. Thus, the estimates of the complete data models are averaged using Rubin's rule (Rubin 1987). Effect sizes will be presented as mean difference with 95% confidence interval.

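### Protocol 11.4.3 names no deciding analysis for urinary, breath and lung-function outcomes, and leads with a change-score test although its power table rests on a baseline-adjusted one

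*Supplement*

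**What the plan says.** Protocol 9.0 section 11.4.3 covers changes in urinary biomarkers, exhaled-breath measures, cardiovascular risk factors (CVRFs), respiratory symptoms and pulmonary function from baseline to 6 months. The arms are first to be compared on these changes "using two-sample t-tests or Wilcoxon rank-sum test, whenever appropriate. We will then fit univariate and multivariate mixed linear effect models". Regression models by exposure to tobacco and ENDS follow. Section 11.4 sets the level for everything: "A significance level of 5% will be used".

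The section does not give the covariates of the multivariate model, the mixed-model coefficient that is read, the rule for choosing t-test or Wilcoxon, or which result decides.

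SAP 2.0 section 4.1 makes tests two-sided. Its section 6.3.1 has one named model: "Continuous secondary outcomes will be analysed using linear models, adjusted for the outcome measure at baseline, if it is available". The continuous outcomes in its section 6.1 are cigarettes per day, CAT and the CVRFs. Biomarker concentrations, breath measures and lung function are not there. Section 6.7 puts subprojects and further outcomes outside the SAP, and section 7 refers additional outcomes back to the protocol.

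**The concern.** Reducing exposure to inhaled toxicants is a secondary objective (protocol 4.3), yet for the outcomes that address it 11.4.3 is the only analysis text, and it offers several tests without ranking them. SAP 2.0 (2.8 and Table 4) and the closing note on changes say that all analyses are done by staff aware of allocation. If the tests disagree, nothing written beforehand settles which one is reported as the answer.

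There is also a mismatch inside the protocol. If the power table assumes one analysis and the text leads with another that has larger variance, the stated power does not belong to the first planned test.

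**Working it through.** **1. Inputs.** From protocol 11.2 and the footnote to Table 11.2-2: "an assumed correlation between baseline and follow-up of 0.7 and 182 participants (112 vs. 70) for urine analyses", alpha 0.05. Urinary 8-OHdG: past smokers 3.62 (SD 2.41), current smokers 4.24 (SD 3.3). The stated power is 48%, with 174 per group for 80%.

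**2. Formulas.** Two-sample normal approximation with unequal SDs and a variance factor f:

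- power = Φ( d / √[f(s₁²/n₁ + s₂²/n₂)] − 1.96 )
- n per group for 80% = (1.96 + 0.8416)² × f × (s₁² + s₂²) / d²
- f = 1 (follow-up value only), f = 2(1−r) = 0.60 (change score), f = 1−r² = 0.51 (baseline-adjusted), with r = 0.7

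**3. Reproducing the table, 8-OHdG.** d = 0.62. s₁²/112 + s₂²/70 = 0.05186 + 0.15557 = 0.20743. s₁² + s₂² = 16.698.

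| Analysis | f | Standard error | Power | n per group |
|---|---|---|---|---|
| Follow-up only | 1 | 0.455 | 27.5% | 341 |
| Change score | 0.60 | 0.353 | 42.0% | 205 |
| Baseline-adjusted | 0.51 | 0.325 | 47.9% | 174 |
| Protocol states | | | 48% | 174 |

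**4. A second row.** 1-OHP, 0.11 (0.11) against 0.20 (0.25): baseline-adjusted gives 97.8% and 36.9 per group (stated 98% and 37); a change score gives 95.7% and 43.4. In both rows only 1−r² reproduces the stated figures.

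**5. What this means for the change score.** The ratio of the factors is (1−r²)/[2(1−r)] = (1+r)/2 = 0.85, so the change-score t-test needs 1/0.85 = 1.18 times as many participants (205/174 = 1.18). Where the adjusted model has 80% power, the change test has 73% at r = 0.7, 68% at r = 0.5 and 62% at r = 0.3.

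**6. False positives if any significant result is accepted.** The tests share data, so they are correlated. For the change t-test and the baseline-adjusted model the correlation is √[(1+r)/2] = 0.922 at r = 0.7. The bivariate normal then gives a chance of at least one p < 0.05 of 6.8% (7.3% at r = 0.5, 7.8% at r = 0.3).

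The full sequence was simulated under no effect (150 per arm, 6,000 runs per case, Monte Carlo error about 0.4 points). Added covariates were assumed to explain 0-40% of residual variance. At r = 0.7:

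- change t-test plus mixed models that test group by time: 5.9-7.5%. With two time points the univariate mixed model duplicates the t-test; a direct check gave t = 0.506 for both.
- change t-test plus baseline-adjusted models, without and with covariates: 7.5-9.8%.

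Over r = 0.3 to 0.7 the range is about 6-10%.

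**7. Protocol against SAP.** For CAT and the CVRFs, 11.4.3 starts from a test on change, while SAP 6.3.1 uses a baseline-adjusted linear model. SAP section 7 says that deviations from the protocol are set out there. Table 4 lists two, outcome definitions and blinding, and not this one.

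**The case against.** The case on the other side is substantial. An unadjusted comparison followed by adjusted models is a common reporting sequence. Section 11.4 asks for effect measures with confidence intervals, and nothing in 11.4.3 says that any one significant result counts as success. These are secondary outcomes whose power the protocol itself calls limited. For CAT and the CVRFs the SAP does name a main model; its section 6.3.6 considers transformation, robust methods or Wilcoxon only if assumptions fail. Subprojects are registered separately, and any plan attached to those registrations cannot be seen here. All of this stands. It limits the size of the point but does not supply the missing label, because the SAP sends the uncovered outcomes back to the protocol.

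Two stronger readings are tempting and are not supported:

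- A reader might infer that the false-positive rate about doubles. That is close to the figure for two independent tests, 1 − 0.95² = 9.75%, but these tests are highly correlated. The protocol offers t-test or Wilcoxon as alternatives, not both. A rate near 10% needs baseline-adjusted models with strong covariates; trying both first-step tests as well gives 8-11% (up to 11.5% with skewed data).
- A reader might infer that the plan leads with the weakest test available. A two-time-point group-by-time mixed model has the same power as the change t-test. In skewed data the Wilcoxon test on change can beat a raw-scale baseline-adjusted model. How skewed these outcomes are is also unclear: the 1-OHP row with mean 0.2 and SD 0.25 is strongly dispersed, but 1-naphthol at 7.2 (0.4) and 8-isoprostane at 1.1 (0.1) are not.

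**Conclusion.** The point holds for urinary biomarkers, exhaled-breath measures and pulmonary function: several tests at 5%, none named as deciding, and no SAP rule to settle it. For CAT and the CVRFs the gap is smaller, an unlisted difference between protocol and SAP.

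Two sizes can be given. The leading change-score t-test has about 42% power where the table states 48% (205 against 174 per group). The per-outcome false-positive rate would be roughly 6-10% instead of 5% if any significant result were accepted.

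The power figures rest on the table's raw-scale means and SDs, on r = 0.7, and on its contrast of quitters with continuing smokers. For the comparison of randomised arms it is the factor 1.18 that carries over, under equal variances at both visits, not the 42% and 48%. The error range rests on an assumed covariate strength and on two time points, as 11.4.3 words it; the synopsis extends these comparisons to 12 and 24 months, which would change the mixed model. The primary smoking-cessation analysis is not affected.

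**What to change.** In protocol 11.4.3, name one deciding analysis per outcome: a linear model of the 6-month value on randomised arm, adjusted for the baseline value on the same scale. Use the log scale for urinary and breath concentrations and report ratios of geometric means. Label the t-test or Wilcoxon comparison, the mixed models and the exposure-group models as supportive, and list the covariates of any multivariate model. Add the CAT and CVRF difference to SAP Table 4, or bring 11.4.3 into line with SAP 6.3.1.

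The cost is wording. Data and software are unchanged, the baseline values are already collected, and the model type is the one in SAP 6.3.1 and the one implied by Table 11.2-2. With one deciding test the rate returns to 5% per outcome. The price is that log-scale results are read as ratios and not as mean differences.

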11.4.4 Interim analyses

No formal interim analysis is planned. We do not anticipate undertaking formal interim analyses in this trial. In particular, even if a significantly large number of participants stop smoking in the intervention group, we will not stop the trial.

11.4.5 Safety analysis

We will compare the proportion of adverse events and serious adverse events between groups using recommended methods.

11.4.6 Deviation(s) from the original statistical plan

Deviations from the statistical analysis plan will be stated and justified in the final analysis report.

11.5 Handling of missing data and drop-outs

Participants lost during follow-up will be categorized as persistent smokers in the intention-to-treat analysis. We intend to obtain full follow-up data on all randomized participants. For missing data on the main and secondary outcomes, we will perform sensitivity analyses computing inverse probability of censoring weights (IPCWs) in the multivariate regression models, modeling the probability of missing data to weight the available measurement. Missing data on covariates will be handled using multiple imputation techniques.

12. QUALITY ASSURANCE AND CONTROL

12.1 Data handling and record keeping / archiving

The Investigators will maintain appropriate medical and research records for this trial, in compliance with ICH-GCP and regulatory and institutional requirements for the protection of confidentiality of subjects. The Principal Investigator, Sub-investigator, and Clinical Research Nurses or Coordinators will have access to the records. The Principal Investigators will permit authorized representatives of the Sponsor and regulatory agencies as applicable to examine clinical records for the purposes of quality assurance reviews, audits, and evaluation of the study safety and progress.

12.1.1 Case Report Forms

The CRF will be electronic. All data requested on the eCRF will be recorded and the investigators will ensure the recorded data will be consistent with the source documents or the discrepancies will be explained. The Investigator will ensure the accuracy, completeness, and timeliness of the data reported in the eCRF and all other required reports. Generally, the eCRF will be completed within two weeks of completion of a participant's visit/ follow-up phone call.

12.1.2 Specification of source documents

Source documents will be available at the site to document the existence of the study participants and will include the original documents relating to the study, as well as the medical treatment and medical history of the participant.

For all data captured in the eCRF, the location of the source will be documented on a list of source documents (source data location list), which will be stored in the investigator site file at each study site.

If certain data are directly entered into the eCRF (and are thus considered as source data) this will be specified on the source data location list accordingly.

Any change or correction to source data will be dated, initialed, and explained (if necessary) and will not obscure the original entry.

12.1.3 Record keeping / archiving

All study data will be archived for a minimum of 10 years after study termination or premature termination of the clinical trial. The Investigators will take measures to prevent accidental or premature destruction of these documents.

12.2 Data management

12.2.1 Data Management System

The CRFs in this trial will be implemented electronically using a dedicated electronic data capturing

(EDC) system (secuTrial). The EDC system will be activated for the trial only after successfully passing a formal test procedure conducted by the CTU Bern. All data entered in the CRFs will be stored on a Linux server in a dedicated Oracle database at the CTU Bern.

Responsibility for hosting the EDC system and the database will lie with Inselspital Bern.

12.2.2 Data security, access and back-up

The server hosting the EDC system and the database will be kept in a locked server-room. Only the system administrators will have direct access to the server. A role concept with personal passwords (site investigator, statistician, monitor, administrator etc.) will regulate permission for each user to use the system and database as he/she requires.

All data entered into the CRFs will be transferred to the database using Secure Sockets Layer (SSL) encryption. Each data point will have attributes attached to it identifying the user who entered it with the exact time and date. Retrospective alterations of data in the database will be recorded in an audit table. Time, table, data field and altered value, and the person will be recorded (audit trail). A multi-level back-up system will be implemented.

We will provide participants with the possibility of filling some questionnaires online themselves. The online questionnaires will be filled by participants through SurveyMonkey. As a global organization, SurveyMonkey is subject to the General Data Protection Regulation (GDPR) in order to protect personal data. The data entered in the surveymonkey will be entered into the dedicated electronic data capturing System by the study nurses of the corresponding study site. No personal data such as name and address will be entered into SurveyMonkey instead the study participants ID will be used for identification.

12.2.3 Analysis and archiving

Final analyses and data files will be extracted from the database into statistical packages to be analyzed. The status of the database at this time will be recorded in special archive tables.

The study database with all archive tables will be securely stored by CTU and Inselspital Bern. The sponsor also will keep the Trial Master File and interim/final reports for at least 10 years.

12.2.4 Electronic and central data validation

Data will be checked by the EDC system for completeness and plausibility. Furthermore, selected data points will be cross-checked for plausibility with previously entered data for that participant. In addition, central data reviews will be performed on a regular basis to ensure completeness of the data collected and accuracy of the primary outcome data.

Before database lock the PI will validate the collected data with his signature.

12.3 Monitoring

For quality control of the study conduct and data retrieval, all study sites will be visited on-site by appropriately trained and qualified Monitors from the CTU Bern. Any findings and comments will be documented in site visit reports and communicated to the local Investigator and to the Sponsor as applicable. Investigators at the participating study sites will support the Monitor in his/ her activities. Prior to study start (first participant enrolled) a plan detailing all monitoring-related procedures will be developed.

All source data and relevant documents will be accessible to Monitors and questions of Monitors are answered during site visits.

12.4 Audits and Inspections

Source data/ documents will be made available to audits by the Sponsor or designee or to inspections by the CEC or regulatory authorities. If an inspection is requested, the Investigator will inform the Sponsor immediately that this request has been made. The Investigators at the participating sites will support the inspectors in their activities and will answer questions from inspectors as needed. All

involved parties will keep the participant data strictly confidential.

